Specific aim #1: Define functional nausea (FN) as an entity subdivided by measures of arousal, anxiety and gastric motor function.

Hypothesis: Adolescents with chronic nausea form subgroups based on clinical, physiologic and psychological parameters: 1) FN: characterized by high anxiety and emotional arousal, autonomic imbalance/low vagal tone and absence of major foregut dysmotility, 2) gastroparesis, and 3) poor gastric compliance. We will separate FN from other groups by clinical questionnaires, autonomic tests (heart rate variability) and gastric motility tests (gastric emptying, accommodation tests).

Specific aim #2: Demonstrate that resting state functional brain connectivity is different in female adolescents with FN compared to gender and age-matched healthy controls.

Hypothesis: Adolescents with FN will have altered rsFC between brain regions associated with emotional arousal neurocircuits (amygdala) and the top-down regulation of these by the prefrontal cortex. There will be decreased resting state functional connectivity between the ventromedial prefrontal cortex (vmPFC) and amygdala in adolescents with FN compared to healthy controls.

Specific aim #3: Demonstrate that four weeks of auricular neurostimulation improves nausea while strengthening the vagal tone and the abnormal resting state brain connectivity in female adolescents with FN compared to baseline and to more resemble that of healthy controls.

Hypothesis: 3a) Compared to baseline (pre-stimulation), there will be reduction in nausea and concurrent symptoms in the active compared to sham neurostimulation group after 4 weeks of therapy. 3b) Active neurostimulation therapy will increase vagal tone compared to baseline and also increase the rsFC between the vmPFC and amygdala in female adolescents with FN.

C. BACKGROUND, SIGNIFICANCE, AND RATIONALE

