Medical and psychological history will be obtained to verify eligibility and screen patients for alcohol, nicotine, and drug abuse following the completion of consent/assent documents. All eligible subjects will complete the questionnaires related to demographic, medical, and psychological factors including nausea, abdominal pain, IBS symptoms (Rome IV), anxiety, disability and quality of life (Table 1). This will take about 30 minutes total to complete. Subjects will then undergo baseline heart rate variability (HRV) measurements in clinic. Children will perform a self-assessment of the Tanner stage of pubertal development using a validated self-assessment form.

Visit 1: Subjects will undergo the ¹³C gastric emptying breath test (GEBT) (Table 1). See section on ¹³C GEBT for details and attached protocol.

Visit 2: Subjects will undergo Satiety Drink Test (see SDT section and attached protocol).

Visits 3-6: Subjects will complete questionnaires as per Table 1 followed by neurostimulator placement by study physician. These visits will be repeated weekly and take about 20-40 minutes to complete. HRV will be measured before and after the EAD placement at Visit 3 and 6.

Post-neurostimulation #1: Subjects will not return but will complete questionnaires (Table 1) at the end of 4 weeks of therapy which will be mailed back to the research team. Participants in fMRI sub-study will undergo repeat fMRI scan (post-scan) at this visit and complete questionnaires per Table 1.

Post-neurostimulation #2: All subjects will return to clinic for their regularly scheduled clinic follow-up visit 2 months after end of therapy and will complete questionnaires as per Table 1.

Subsequent to the initial 4 weeks of therapy, subjects will undergo another 4 weeks of **active neurostimulation therapy (visits 7-10) with the exact same protocol as during the first round of treatment. A post-neurostimulation #3 questionnaire assessment will be completed (just as with post-neurostimulation #1) although no repeat fMRI scans will be performed at this time. Similarly, a post-neurostimulation #4 clinic visit will be scheduled 2 months after the end of the second 4 week of therapy.

Optional fMRI Sub-study

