| Screening & Consent | x | | | | | | | |
| Tanner staging | x | | | | | | | |
| ¹³C gastric emptying breath test | | x | | | | | | |
| Satiety Drink Test | | | x | | | | | |
| Heart Rate Variability | x | | | x ¹ | | x ¹ | | |
| Nausea Profile | x | | | x | x | x | x | x |
| BARF scale | x | | | x | x | x | x | x |
| SUDS scale | x | | | x | x | x | x | x |

| | | | | | | | | |
|---|---|--|--|---|---|---|---|---|
| API (pain and nausea) | x | | | x | x | x | x | x |
| PROMIS anxiety & global health | x | | | x | x | x | x | x |
| FDI | x | | | x | x | x | x | x |
| Nausea Severity Scale | x | | | x | x | x | x | x |
| CSI | x | | | x | x | x | x | x |
| VSI | x | | | x | x | x | x | x |
| PAGI-SYM | x | | | x | x | x | x | x |
| ROME IV | x | | | | | | | |
| Symptom response scale | | | | | x | x | x | x |
| Neurostimulator (active or sham) | | | | x | x | x | | |
| fMRI scan (subset) | | | | x | | | x | |

NP=Nausea Profile; API=Abdominal Pain Index; PROMIS= Patient Reported Outcome Measurement Information System; FDI=Functional Disability Inventory; CSI=Children's Somatization Inventory; VSI=Visceral Sensitivity Index; PAGI-SYM=Patient Assessment of Upper Gastrointestinal Symptom Severity Index

x¹ HRV will be completed prior to and after neurostimulator placement.

All procedures will be performed in the Children's Hospital of Wisconsin (CHW) Pediatric Translational Research Unit (pTRU). Prepackaged kits (Cairn Diagnostics, Brentwood, TN, USA) for the gastric emptying breath test and nutrient drinks will be stored by research coordinators in locked offices within the Division of Gastroenterology and brought to the pTRU on the day of testing. The prepackaged kits for the gastric emptying test and neurostimulators will be shipped by manufacturer when requested by PI. A box labeled with subject ID and containing neurostimulators (four), a GEBT kit and a labeled folder with patient ID and relevant questionnaires will be premade and kept with each subject package. After the breath test is performed, research coordinators will ship the samples to Cairn Diagnostics within 2 days of collection.

Measurements and Data Collection

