Subjects will be randomized in a 1:1 ratio to either treatment or sham group. Randomization will be determined using a computer program based on random number generation in blocks of 10 subjects at a time. The manufacturer will provide the researchers with four devices per package (4 weeks per patient) and distribute 10 packages at a time to the investigators. Each package will have a serial number and only one research coordinator will have the key to which serial numbers represent active devices and which represent inactive ones. This research coordinator will keep the data in a secure database and will not be involved in any of the patient recruitment or study procedures. All other research coordinators, investigators, statistician and nurses involved will be blinded. Research coordinators within the division of gastroenterology will store the devices as pre-packaged by manufacturer and label the devices with a serial number and patient ID number. A labeled folder for each patient with all questionnaires needed for the entire study will also be kept with each subject package. The devices and folders will be stored in a locked office in the gastroenterology division, only accessible by research coordinators. Password protected iPads will be used to collect questionnaire information from participants. No PHI will be loaded on these iPads.

A blinded research coordinator will bring each subject's numbered package to the research area (Translational Research Unit) when patient arrives. The package for the subject will be stored locked in the TRU until the subject finishes the 4 week therapy. The coordinator will ask the subject to complete the pre-placement questionnaires (Table 1; visit #3) and hand the device (numbered with serial # and patient ID only) to one of the certified MDs for placement. The devices will be "made to order" when requested by the PI and will be shipped packaged as above.

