Aim 3. *Hypothesis 3a): Four weeks of active neurostimulation will reduce nausea and concurrent symptoms from baseline compared to sham therapy as measured by weekly Nausea Severity Scale total score (primary outcome) after 4 weeks of therapy. Secondary outcomes include daily nausea (BARF) scores, and weekly nausea profile scores, upper GI symptoms (PAGI-SYM), abdominal pain (API), anxiety (SUDS, PROMIS and VSI), quality of life (PROMIS), disability (FDI) and co-morbid symptoms (CSI).* Another secondary efficacy variable will be the change in Nausea Severity Scale score after the second 4 weeks of therapy in a subset of subjects. We will compare pre and post total nausea, GI symptoms, anxiety, disability, quality of life and co-morbid symptom scores using a two-sided paired *t*-test at a Bonferroni corrected alpha of 0.05. Power: with ~40 in each group initially, allowing for 12% dropout based on our prior study, we will have ~35 subjects and 80% power to detect a difference of at least XX standard deviations (SD). We will similarly compare the other variables. Further we will use regression and regression trees with final value as the outcome and demographics, baseline values and overall symptoms as covariates. *Hypothesis 3b: Adolescents with FN will have reduced vagal tone as measured by HRV. Active neurostimulation therapy will elevate vagal tone compared to baseline and sham therapy, resembling that of healthy controls.* We will similarly analyze the change in vagal tone in nausea subjects. Further we will compare

the final vagal tone to healthy using a two sample t-test of equivalence where equivalence will be defined as within 20%. See fMRI analysis section for details on resting state fMRI analyses.

Longitudinal Continuous Variables

The efficacy parameters of longitudinal continuous variables such as nausea and pain will be analyzed using a mixed effects covariance pattern model to utilize all the data collected over time with consideration of the variance-covariance matrix of the repeated measures. This method allows a general unstructured variance-covariance matrix and allows patients to have incomplete data across scheduled time points. The method applied is also known as mixed-effects repeated measures analyses (MMRM).

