The primary model will include independent variables of the fixed, categorical effects of treatment, assessment visit, and treatment-by-assessment, interaction, along with the continuous effects of baseline and baseline-by-assessment interaction up to end of study. An unstructured variance-covariance structure will be used to model the within-patient errors and different variance-covariance structures will be tried for goodness-of-fit exploration.

Continuous/ Ordinal variables

Summary statistics such as mean, median, standard deviation, range and correlation plots and tree analysis will be used to examine distributions and interrelationships. Where necessary, for parametric assumption, we will employ appropriate transformations with justifications. If data cannot be appropriately transformed we will compare variables between the two groups using a Mann-Whitney test.

Additional Analysis

In addition to the above described primary analysis, the following analysis will be done.

1. The mean change from baseline in all efficacy variable scores will be summarized using descriptive statistics at all assessment time points.
2. To assess effects of dropouts, the dropout cohort analysis will be performed by summarizing the change of primary and secondary efficacy variables using different dropout cohorts. Dropout cohorts will be formed by patients that had their last primary efficacy measurement in the same assessment interval.

For all efficacy variables, nominal p-values will be presented without applying any adjustment for multiple comparisons.

GEBT Metrics

The preferred and FDA approved GEBT metric is the Percent Dose (abbreviated PCD) excreted at time t after consumption of the test meal. To provide a more convenient scale, we multiply PCD by 1000 to produce kPCD at any time, t.

$$kPCD_t = \left[\frac{DOB * CO_2 PR * R_s * 13}{10 * dose} \right] * 1000$$

where:

- DOB = The measured difference in the ratio [$^{13}\text{CO}_2/^{12}\text{CO}_2$] between a post-meal breath specimen at any time (t-minutes) and the baseline breath specimen.
- CO₂PR = CO₂ Production Rate (mmol CO₂/min) calculated using the Schofield equations⁹⁷ which incorporate the patient's age, gender, height and weight.
- R_s = The ratio [$^{13}\text{CO}_2/^{12}\text{CO}_2$] in the reference standard (Pee Dee belemnite) for these measurements. R_s = 0.0112372
- 13 = the atomic weight of Carbon-13
- 10 = A constant factor for converting units

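### Most symptom scales, including the primary one, are scored twice before the first device, but the analysis does not say which score is baseline or whether Visit 3 is an outcome visit

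*Combined protocol and SAP*

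**What the plan says.** Table 1 in section F schedules the primary outcome at six columns: "Nausea Severity Scale | x | | | x | x | x | x | x". Read against the column heads, these are Pre, Visit 3, Visits 4-5, Visit 6, Post #1 and Post #2. The Nausea Profile, BARF, SUDS, API, PROMIS, FDI, CSI, VSI and PAGI-SYM follow the same pattern. Two instruments do not. The symptom response scale starts after treatment ("Symptom response scale | | | | | x | x | x | x"), and Rome IV is taken only at Pre.

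The Visit 3 scores are pre-treatment. Protocol and Procedures (section D) says of Visits 3-6: "Subjects will complete questionnaires as per Table 1 followed by neurostimulator placement by study physician". The treatment protocol in section F has the coordinator ask the subject to "complete the pre-placement questionnaires (Table 1; visit #3" and then hand the device over for placement.

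The label of baseline sits on the earlier visit. In section D the heading over the enrolment visit adds the word Baseline to Pre, and at that visit "All eligible subjects will complete the questionnaires related to demographic, medical, and psychological factors including nausea, abdominal pain" and other symptoms.

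The Statistical Analysis section names no visit. Under Aim 3 it says "We will compare pre and post total nausea, GI symptoms, anxiety, disability, quality of life and co-morbid symptom scores", by paired t-test. Longitudinal Continuous Variables specifies a repeated-measures model on all data collected over time, with treatment, visit and their interaction, "along with the continuous effects of baseline and baseline-by-assessment interaction up to end of study". Additional Analysis adds summaries of mean change from baseline at every time point.

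**The concern.** Pre is the gastroenterology clinic visit at which the family is recruited. The breath test and the drink test, on separate fasting mornings, fall between it and the first device, and no maximum interval is set. Patients recruited at a clinic visit while refractory to therapy may improve somewhat before anything is done to them.

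If the section D label is carried into the analysis, three things follow. Improvement before the first device enters the paired tests and the change-from-baseline summaries as change on therapy. The model adjusts for the older score alone, although a later pre-device score exists for the same subjects. And Visit 3 can enter as an outcome visit, with a treatment-by-visit term for a device not yet placed. If the definition is left open, the choice could also be made after the data have been seen.

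**Working it through.** **The plan's own figure.** Power, Aim 3, starts with about 40 per group and allows 12% dropout: 40 × (1 − 0.12) = 35.2, so the stated figure of about 35 reproduces. The detectable difference is printed as XX. At two-sided 0.05 and 80% power without covariates it would be √(2/35) × (1.960 + 0.842) = 0.67 SD between arms (normal approximation).

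**Assumptions.** The documents give no correlations, no pre-device drift and no interval. Write r_P and r_V for the correlations of the Pre and Visit 3 scores with the week-4 score, and r_B for the correlation between the two. Scores have SD 1.

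**1. Within-arm paired test, no device effect.** n = 35 and pre/post correlation 0.5, so the SD of change is √(2 × (1 − 0.5)) = 1. With Pre as reference, a drift of d SD before the first device gives a noncentral t with noncentrality d√35 on 34 df.

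| Assumed drift (SD) | Share of trials with p < 0.05 |
|---|---|
| 0 | 5% |
| 0.1 | 9% |
| 0.2 | 21% |
| 0.3 | 41% |
| 0.5 | 82% |

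With Visit 3 as reference the drift drops out and the rate is 5%.

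**2. Randomised contrast.** A simulation used 20,000 trials with 35 per arm, r_P = 0.5, r_V = 0.6, r_B = 0.7, a 0.3 SD drift in both arms and no device effect. Adjusting for Pre, the mean arm difference was −0.001 SD, type I error 4.9% and SE 0.208. Adjusting for Visit 3, type I error was 5.0% and SE 0.192. There is no bias. The squared SE ratio, (0.192/0.208)² = 0.85, matches (1 − 0.6²)/(1 − 0.5²) = 0.64/0.75 = 0.85.

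**3. Both scores as covariates.** Residual variance with Pre alone is 1 − r_P². With both it is 1 − (r_P² + r_V² − 2 r_P r_V r_B)/(1 − r_B²).

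| r_P | r_V | r_B | Pre alone | Both | Cut |
|---|---|---|---|---|---|
| 0.5 | 0.5 | 0.8 | 0.750 | 0.722 | 4% |
| 0.5 | 0.5 | 0.7 | 0.750 | 0.706 | 6% |
| 0.5 | 0.5 | 0.6 | 0.750 | 0.688 | 8% |
| 0.4 | 0.5 | 0.6 | 0.840 | 0.734 | 13% |
| 0.5 | 0.6 | 0.7 | 0.750 | 0.627 | 16% |

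In the last row the detectable difference falls from 0.67 × √0.750 = 0.58 SD to 0.67 × √0.627 = 0.53 SD. Less favourable values for Pre raise the cut: (0.5, 0.6, 0.6) gives 1 − 0.609/0.750 = 19%, and (0.4, 0.6, 0.6 to 0.8) gives about 24% to 26%. Visit 3 alone in place of Pre gains nothing if r_P = r_V.

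**4. Visit 3 as an outcome row.** With complete data, a full treatment-by-visit interaction and Pre as covariate, the Post #1 contrast equals the covariance analysis on Pre alone, so Visit 3 adds no precision there. If the effect were averaged over visits, a constant device effect would shrink to 4/5 = 80% (Visits 3, 4, 5, 6 and Post #1) or 5/6 = 83% (adding Post #2).

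**The case against.** A reader might infer that the plan fixes enrolment as the analysis baseline and so biases the primary result. The documents support neither step.

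- The model sentence names no visit; the label comes from a procedures heading. Hypothesis 3a says "Compared to baseline (pre-stimulation), there will be reduction in nausea and concurrent symptoms in the active compared to sham neurostimulation group", which fits Visit 3 equally well, and section D treats the Visit 3 fMRI scan as the baseline scan. Strictly, baseline is undefined between two candidates.
- Allocation is 1:1 and blinded, so drift before the device is common to both arms and cancels in the active versus sham contrast. The simulation confirms this.
- The Visit 3 score is not strictly discarded, because the model uses all data. Dilution would arise only if effects were averaged over visits, which the plan does not say.
- Drift may be small. Entry rests on Rome IV criteria and not on a minimum nausea score, and patients with a regimen change in the previous four weeks are excluded.

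These points stand and limit the concern. They do not remove it. The paired test is the one stated under Hypothesis 3a, the only questionnaire visit labelled baseline is Pre, and no sentence gives the Visit 3 symptom scores a role as baseline or excludes them as outcomes.

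**Conclusion.** The point holds as an undefined symptom baseline with a free improvement available. Its effect differs by analysis. For within-arm paired tests and change-from-baseline summaries, following the label credits therapy with change that precedes it: 21% to 41% false positives per test for an assumed drift of 0.2 to 0.3 SD (n = 35, correlation 0.5). For the randomised contrast the cost is precision only: about 4% to 16% of residual variance in the main assumed cases, up to about 26% if Visit 3 predicts much better than Pre. All of these figures rest on assumed correlations and drift. The point covers scales taken at both visits, so it does not extend to the symptom response scale or Rome IV. It should be settled before unblinding, but it does not threaten the validity of the active versus sham comparison.

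**What to change.** Amend the Statistical Analysis section as follows, for every scale taken at both Pre and Visit 3:

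1. Use the Visit 3 pre-placement score as the reference for paired tests and change-from-baseline summaries, with Pre as substitute if Visit 3 is missing.
2. In the repeated-measures model, enter the Pre and the Visit 3 score as two baseline covariates, each with its by-visit interaction. State how a missing one is filled without using treatment or later outcomes.
3. Start the repeated outcome at Visit 4.
4. Relabel the Pre column and heading as screening for these scales.

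Do not average the two scores as the reference for change, because half the drift would remain. For r_B from 0.6 to 0.8 the SD of change is √((1 + r_B)/2), or 0.89 to 0.95. A 0.2 SD drift then still gives 9% to 10% false positives and a 0.3 SD drift 15% to 16%, against 5% with Visit 3.

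The cost is wording only. Both scores are already scheduled for every treated subject, and no visit or questionnaire is added.

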fMRI-guided connectivity analysis: We have developed a novel *fMRI-guided connectivity analysis* in previous investigations by [name] to determine the distribution of an arousal network by using a seed region in a specific brain area of interest. In this protocol, we will examine resting state functional connectivity with amygdala as the seed region of interest and its coupling with prefrontal cortex areas as well as insula and hypothalamus as key nodes of the emotional arousal neurocircuit and internal awareness.

Statistical Analysis

Data Management

The data gathered will be entered into REDCap data system with each ID having a unique identifier for each participant. REDCap is a secure, web-based application for building and managing online databases. All data will be de-identified and samples will only have a unique identifier that will link the unique identifier with the patient's name.

The REDCap clinical database will be maintained by the Department of Quantitative Health Sciences, at the Children's Research Institute under the direction of [name].

Missing Data Handling

Missing Data: Every effort will be made to avoid missing data. Using logistic regression, the pattern of missing data will be explored. Assuming the data are missing at random (MAR) multiple imputations for items will be used. Data analysis overview: Summary statistics, such as mean, median, standard deviation, range and correlation will be used as a first step to examine data. To satisfy parametric assumptions, we may perform transformations with justifications if possible and otherwise use non-parametric tests. We will use CART and biological and physiological information to identify interactions when formulating regression models. Statistical software employed for data analysis will be: Cytel StatXact, SAS version 9.4, Salford System CART for trees, SPSS Version 24. The power calculation was made using PASS 13.'

Power

Aim 1. We will summarize characteristics by the groupings.

Aim 2. See fMRI analysis section below

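### The fallback for data that resist transformation is an unadjusted Mann-Whitney test; a baseline-adjusted rank analysis would be equally valid, more efficient and free

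*Combined protocol and SAP*

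**What the plan says.** Four parts of the Statistical Analysis text in section F of the combined protocol and SAP bear on this.

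- **Longitudinal Continuous Variables.** The primary model is a mixed model for repeated measures (MMRM) with treatment, visit and their interaction, "along with the continuous effects of baseline and baseline-by-assessment interaction up to end of study". One reason given for choosing it is that it "allows patients to have incomplete data across scheduled time points".
- **Continuous/ Ordinal variables**, the next heading: "If data cannot be appropriately transformed we will compare variables between the two groups using a Mann-Whitney test". No covariate, stratum or visit is named. The text does not say whether the test is run on the final score or on change from baseline.
- **Missing Data Handling.** The same rule appears in general terms: "To satisfy parametric assumptions, we may perform transformations with justifications if possible and otherwise use non-parametric tests". No criterion is given for when a transformation has failed.
- **Power, Aim 3.** The primary outcome is defined "as measured by weekly Nausea Severity Scale total score (primary outcome) after 4 weeks of therapy". A further analysis is listed: "Further we will use regression and regression trees with final value as the outcome and demographics, baseline values and overall symptoms as covariates". It uses baseline, but it is not described as the fallback for non-normal data.

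Table 1 shows the Nausea Severity Scale and the other symptom scales collected at Pre and again at Visit 3, before the first device is placed. The symptom response scale starts only at Visits 4-5.

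**The concern.** The plan adjusts for baseline in its main model and drops that adjustment in the only non-parametric alternative it names. The alternative could well be needed. Several efficacy scales are bounded (BARF and SUDS run from 0 to 10), and if nausea improves, scores may pile up at the low end, where no transformation helps. The baseline score is already in hand, so leaving it out saves nothing.

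What is at stake is precision: power is lost if baseline predicts the week-4 score, and a chance baseline difference between two arms of about 35 is left uncorrected in that comparison. There is also a pre-specification gap, because final-value and change-score versions of the test differ in power and the choice between them is left open.

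**Working it through.** **Inputs from the documents.** Allocation is 1:1. On numbers: "with ~40 in each group initially, allowing for 12% dropout based on our prior study, we will have ~35 subjects". Check: 40 × (1 − 0.12) = 35.2, which agrees. The plan's 80% power cannot be reproduced because the effect size is shown only as XX; this may be a placeholder or removed text and is not treated as an error. For scale, a two-arm comparison with 35 per arm, two-sided 0.05 and 80% power detects (1.96 + 0.84) × √(2/35) = 0.67 SD.

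**Assumed, because the documents do not say.** Effect 0.5 SD on the underlying scale; correlation between baseline and week 4 of 0, 0.3, 0.5 or 0.7; scores that are normal, log-normal, or on a 0-10 scale with a floor; two-sided 0.05.

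**Step 1, normal-theory guide.** Baseline adjustment multiplies the outcome variance by 1 − ρ². Power = Φ(0.5 / √((1 − ρ²) × 2/35) − 1.96).

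- ρ = 0: Φ(2.09 − 1.96) = 55%
- ρ = 0.3: Φ(2.19 − 1.96) = 59%
- ρ = 0.5: Φ(2.41 − 1.96) = 68%
- ρ = 0.7: Φ(2.93 − 1.96) = 83%

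The gains over no adjustment are 4, 12 and 28 points.

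**Step 2, simulation of the rank tests.** Quade's method regresses the ranks of the week-4 score on the ranks of the baseline score and compares the residuals between arms.

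| Correlation | Log-normal: Mann-Whitney, final score | Log-normal: Quade | Floor-limited 0-10: Mann-Whitney, final score | Floor-limited 0-10: Quade |
|---|---|---|---|---|
| 0 | 52% | 52% | 48% | 48% |
| 0.3 | 52% | 55% | 48% | 52% |
| 0.5 | 52% | 63% | 48% | 57% |
| 0.7 | 52% | 79% | 48% | 71% |

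The log-normal columns use 4,000 trials per setting, so the Monte Carlo standard error is about √(0.5 × 0.5 / 4,000) = 0.8 points. Across repeat runs and the three score shapes, the gain is about 0, 3 to 4, 8 to 11, and 22 to 27 points. Type I error was near 5% for both tests.

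**Step 3, does skewness matter?** Both tests use only ranks, so exponentiating normal scores changes neither p-value. Normal data gave Quade 62% at correlation 0.5 and 77% at 0.7, the same as log-normal data within simulation error.

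**Step 4, change scores.** Mann-Whitney on change gave 31%, 39%, 52% and 72% at correlations 0, 0.3, 0.5 and 0.7. That is below Quade every time. It is below the final-score test at 0 and 0.3, level at 0.5 and above it at 0.7.

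**Step 5, a larger effect.** At 0.67 SD with log-normal scores, Mann-Whitney on the final score against a rank ANCOVA fitted in one step gave 76% v 79% at correlation 0.3, 77% v 86% at 0.5 and 77% v 95% at 0.7. The pattern is the same.

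**The case against.** The strongest reply is that the plan does not say Mann-Whitney replaces the primary model. The test stands under its own heading, while nausea and pain are assigned to the MMRM. That is correct. A reader might infer a switch for the Nausea Severity Scale, but no sentence states one. What stands is that the scope is unstated and that this is the only named non-parametric route.

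Second, some variables have no baseline to adjust for. The symptom response scale is itself a rating of change, and the gastric emptying and satiety drink tests are done once. An unadjusted rank test is ordinary there, and the fix leaves it in place.

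Third, baseline may not be discarded at all. The text says only that variables will be compared, and Hypothesis 3a is framed as a reduction from baseline, so the test might be run on change. Step 4 shows that this reading does not recover the lost efficiency. The separate regression with baseline as covariate would show whether imbalance matters, but it is not offered as the answer when parametric assumptions fail.

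Fourth, the benefit is uncertain. At correlation 0.3 it is 3 to 4 points, and the documents do not give the correlation. This stands as a limit on the size of the point. Quade's method showed no power cost at correlation 0, so little is risked by adopting it.

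A reader might also infer that power is lost precisely when data are skewed. Step 3 contradicts that: the loss follows the baseline correlation. Skewness matters only because it can trigger the fallback, and log-normal data would be rescued by a log transformation under the plan's own rule. Nor does the argument favour keeping the raw-scale adjusted model with permutation or bootstrap inference. With log-normal scores and a 0.5 SD effect, permutation ANCOVA on the raw scale had about 41% power at correlation 0.3 and 46% at 0.5, against 51 to 52% for Mann-Whitney. It led only at 0.7 (57% v 51%).

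**Conclusion.** The point holds as a minor, free improvement. The written fallback lacks the baseline adjustment that the plan itself chose for its main model, and no other sentence supplies an adjusted fallback. The test remains valid; the loss is one of efficiency, with some looseness in pre-specification. With 35 per arm, a 0.5 SD effect and two-sided 0.05, the power forgone is nil at zero baseline correlation, small at 0.3, 8 to 11 points at 0.5 and 22 to 27 points at 0.7. The effect size, correlations and score distributions are assumptions. The documents do not support a claim that the primary analysis will be replaced, or that the loss is peculiar to skewed data.

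**What to change.** Reword the fallback under Continuous/ Ordinal variables as follows.

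1. For efficacy variables measured before treatment, use Quade's rank analysis of covariance of the week-4 score on the baseline score, and name which pre-treatment reading (Pre or Visit 3) is the baseline.
2. State that this applies to the Nausea Severity Scale if the assumptions of the MMRM fail, and give the criterion for that.
3. Keep Mann-Whitney for variables with no baseline, such as the symptom response scale.
4. Say how subjects without a week-4 score are handled, since a single-visit rank analysis does not use partial follow-up as the MMRM does.

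The cost is a few sentences in the SAP, settled before unblinding. No new data, visits or subjects are needed.
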